3.5.2 Cumulative dose and average daily dose

Cumulative dose for any component of study treatment is defined as the total dose of the medication given during the study treatment exposure.

Average daily dose is defined as [Cumulative dose (mg) / Number of dosing days]; drug free day(s) are not counted as dosing days.

Cumulative dose and average daily dose will be summarized using descriptive statistics by treatment arm for each component of study treatment. Patients with no exposure to the study treatment component will be excluded from the corresponding summary.

3.5.3 Dose intensity and relative dose intensity

Dose intensity (DI) for patients with non-zero duration of exposure to each study treatment component is defined as follows:

For tamoxifen, letrozole, and anastrozole, DI is defined as

DI (mg/day) = Cumulative dose (mg) / duration of exposure to study treatment component (days).

For goserelin, DI is defined as

DI (mg/28 days) = Cumulative dose (mg) / {[(date of last administration of goserelin + 27) – (date of first administration of goserelin) + 1] / 28},

to account for the goserelin dosing schedule in the DI computation.

For ribociclib/placebo, DI is defined as

$DI \text{ (mg/day)} = \text{Cumulative dose (mg)} / \text{adjusted duration of exposure to ribociclib/placebo (days)}$,

where *adjusted* duration of exposure (days) to ribociclib/placebo represents the number of ribociclib/placebo dosing days a patient would be expected to have received per protocol, given their duration of exposure to ribociclib/placebo as defined in [Section 3.5.1](#). Since ribociclib/Placebo follows a 3-weeks on, 1-week off schedule, the adjusted duration of exposure to ribociclib/placebo is the duration of exposure to ribociclib/placebo minus the planned off days. The adjusted duration of exposure to ribociclib/placebo is therefore $21 \times (\# \text{ completed } 28 \text{ day cycles}) + \min(21, \text{duration of last incomplete cycle})$.

For example, if the duration of exposure to ribociclib/placebo is 66 (corresponding to two cycles and 10 days), then the adjusted duration of exposure to ribociclib/placebo is $21 \times 2 + 10 = 52$. If the duration of exposure to ribociclib/placebo is 108 days (corresponding to three cycles and 24 days), then the adjusted duration of exposure is $21 \times 3 + 21 = 84$ days.

Specifically, let D1 represent the duration of exposure to ribociclib/placebo as defined in [Section 3.5.1](#). Then the adjusted duration of exposure is defined as

$D = 21 \times [D1/28] + \min(21, D1 - 28 \times [D1/28])$ days,

where $[x]$ stands for the integer part of x . In this equation $[D1/28]$ is the number of completed cycles, and $D1 - 28 \times [D1/28]$ is the additional number of days in the last, incomplete cycle (if any). For example, if $D1 = 30$ then $[D1/28] = 1$, $D1 - 28 \times [D1/28] = 2$, and $D = 23$. If $D1 = 7$ then $D = 7$; if $D1 = 22$ then $D = 21$; if $D1 = 28$ then $D = 21$, etc.

Planned dose intensity (PDI) is defined as the assigned dose by unit of time planned to be given to patients as per protocol. The PDI for each study treatment component is displayed in [Table 3-1](#). Note that DI will also be calculated and reported in the units displayed in [Table 3-1](#), whereas duration of exposure itself will be summarized in months.

Table 3-1 **Planned dose intensity**

Medication	PDI (dose unit/unit of time)
Ribociclib/placebo	600 mg/day
Tamoxifen	20 mg/day
Letrozole	2.5 mg/day
Anastrozole	1 mg/day
Goserelin	3.6 mg/28 days

Relative dose intensity (RDI) is defined as:

$RDI = DI \text{ (dosing unit / unit of time)} / PDI \text{ (dosing unit / unit of time)}$.

DI and RDI will be summarized separately for each of the study treatment components.

3.5.4 Dose reductions, or interruptions

The number and percentage of patients with dose reductions, interruptions or delays, and the reasons, will be summarized by treatment arm as outlined below for double-blind on-treatment period. The dosage administration record of ribociclib will be listed for cross-over open-label ribociclib plus NSAID plus goserelin treatment for the cross-over on-treatment period.

Interruption: An interruption is defined as a 0 mg dose given on one or more days during the period where a patient is not on the “off” part of a treatment cycle, after which > 0mg dose resumes. For patients who had dose interruption checked but never resumed non-zero dose, the dose interruption will not be counted. For example, in the sequence of 600 mg – 0mg (dose break) – 0mg (dose interruption) – 0 mg (dose permanently discontinuation) the 0mg (dose interruption) will not be counted as dose interruption. Interruptions will be summarized for each component of the study treatment.

Reduction: A reduction is defined as a decrease from the previous non-zero dose to another non-zero dose less than protocol planned dose, even if this decrease has been directly preceded by an interruption. For example, in the sequence of ribociclib 600mg – 0mg – 400mg, the 400mg dose will be counted as a reduction.

If due to dosing error, a patient took a dose during the dosing break with a dose that is lower than the previous dose, this will not be considered as dose reduction. For example, a patient took 600 mg from day 1-21, and mistakenly took 200 mg per day on day 22-28 which is supposed to be a dosing break. The patient resumed 600 mg dosing on day 29. This will not be considered as dosing reduction.

Dose reductions and interruptions will be tabulated separately. Dose escalations are not allowed according to the protocol and will not be counted in these summaries.

Missing data: If dose is recorded but frequency is missing or entered as ‘none’, it is assumed that the study drug was taken as per-protocol.

3.5.5 Discontinuation of study treatment components

The reasons for discontinuation of each study treatment component will be summarized by treatment arm for the double-blind on-treatment period, based on the information on the component DAR CRF for patients who have the “dose permanently discontinued” box checked.

Partial discontinuation: Partial discontinuation refers to discontinuation of ribociclib/placebo or goserelin, respectively, while continuing on study treatment.

For ribociclib/placebo, partial discontinuation is defined as the event when the last non-zero dose of ribociclib/placebo is more than 21 days before the last non-zero dose of study treatment, with the permanent discontinuation box checked in the ribociclib/placebo DAR page.

For goserelin, partial discontinuation is defined as the last non-zero dose of goserelin plus 27 days being more than 21 days before the last non-zero dose of study treatment, with the permanent discontinuation box checked on the goserelin DAR page.

Partial discontinuation of ribociclib/placebo will be summarized by treatment for the double-blind on-treatment period.

The reasons for discontinuation and partial discontinuation will be listed using the cross-over analysis set separately.

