## Amendment 7 (08-Jan-2020)

Study CLEE011E2301 was initiated in November 2014 and completed enrollment on 01-Aug-2016 with a total number of 672 randomized patients. The study met its primary endpoint of progression-free survival (PFS) at the time of the primary analysis in October 2017. The study met its key secondary endpoint of overall survival (OS) at the time of the planned second OS interim analysis in February 2019. As of 08-Jan-2020, there are still 114 patients ongoing on study treatment, including 79 patients on the ribociclib arm and 35 patients on the placebo arm, of which 8 have crossed-over following Amendment 6.

The main purpose of this amendment is to include information on:

- i. Interstitial Lung Disease (ILD)/pneumonitis—ILD/pneumonitis has been observed with CDK4/6 inhibitor treatment (Please refer to IB ed.14 for more information) [Table 6-6](#), LEE011 dose adjustment and management recommendation for ILD/pneumonitis, has been added to the protocol section and listed in ICF as a risk.
- ii. Toxic Epidermal Necrolysis (TEN)—TEN has been reported in the post-marketing setting in a well-documented literature case report. No case was observed in the clinical trials (please refer to IB ed.14 for more information). The Program Standard Language (PSL) updates the Protocol [Section 6.3.1.8](#) guidance for all other adverse reactions, including a specific guidance to discontinue ribociclib if TEN is diagnosed and Informed Consent language updates with relevant information on TEN. Other changes that were made during this update are as follows:
  - Clarify cross over opportunity in the study design
  - Clarify tamoxifen washout requirement
  - Updated both [Table 14-1](#) ‘List of prohibited medications during study treatment’ and [Table 14-2](#) ‘List of medications to be used with caution during study treatment’
  - Other administrative changes throughout the document as indicated in the track changes version of the current program standard language

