## Amendment 6 (18-Jul-2019)

Study CLEE011E2301 was initiated in November 2014 and completed enrollment on 01-Aug-2016 with a total number of 672 randomized patients. The study met its primary endpoint of progression-free survival (PFS) at the time of the primary analysis in October 2017. The study met its key secondary endpoint of overall survival (OS) at the time of the planned second OS interim analysis in February 2019. Given these results, study participants will be unblinded in preparation for study closure. In addition, patients who are still receiving study treatment in the placebo arm, will be allowed to cross over to the ribociclib arm, based on the Investigator's judgement and an individualized benefit risk decision.

As of 03-July-2019, there are still 135 patients ongoing on study treatment, including 89 patients on ribociclib and 46 patients on placebo.

The purpose of this amendment is to:

- i. Unblind patients and investigators in order to allow for knowledge of patient's current treatment allocation
- ii. Allow for patients receiving placebo the opportunity to cross over to treatment with LEE011 per Investigator discretion
- iii. Provide guidance for patients receiving placebo + tamoxifen, who as per Investigator discretion will cross over to LEE011, to switch to an NSAID, if they are to cross over to treatment with LEE011. These patients will complete a wash out period of 5 half-lives.
- iv. Clarify end of study (EOS) and include information on post-study drug access
- v. Specify that central safety assessments can cease and all laboratory and ECG assessments should be performed locally and clarify the frequency of assessments
- vi. Specify that patient reported outcome (PRO) measures should no longer be collected  
[REDACTED]
- viii. Update the laboratory assessments to remove phosphorous and, per the IB, add serum pregnancy testing at EOT

Following this protocol amendment and the unblinding of study participants, the word "placebo" refers to the original treatment allocation in the study. Physical placebo capsules no longer need to be administered but the wording has been kept in places in the protocol to avoid confusion.

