Patients who are currently taking placebo in combination with tamoxifen (and goserelin), that request cross over to LEE011 combination treatment, must switch their endocrine partner from tamoxifen to an NSAI; either letrozole or anastrozole per Investigator decision, prior to crossing over to LEE011. There needs to be a 35-day (5 half-lives) washout period from tamoxifen before starting LEE011, during which time the patients will be taking NSAI plus goserelin only. The rationale for this change in the background endocrine therapy is based on the increased incidence of significant QT prolongation events for the combination of tamoxifen and LEE011 observed in the primary analysis of this study and, as such, the combination of ribociclib and tamoxifen is not recommended. This consideration does not apply to patients originally randomized to LEE011 plus tamoxifen and remaining on study treatment, as for those patients

any QT prolongation events have been managed via LEE011 dose modifications (Table 6-5). Those patients on the placebo arm who do not wish to cross-over from placebo to LEE011 can remain on their current treatment allocation.

All of the study treatment cross-over changes will be managed by the study IRT system. Endocrine partner treatment will be managed locally.

Unblinded study treatment period will conclude once a patient discontinues from the study treatment for any reason or the EOS is declared, whichever occurs first.

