At the time of protocol amendment 6, minimal follow up for all patients on study treatment is 36 months. Central laboratory hematology, biochemistry and ECG assessments will cease and all tests should be performed locally. Patients originally randomized to the LEE011 arm and continuing with open label LEE011 plus endocrine treatment and patients in the placebo arm that elect to continue with their current treatment (i.e. endocrine treatment alone), should have safety assessments and clinic visits as frequently as clinically indicated, but not less frequently than every 12 weeks. Tumor assessments will continue as clinically indicated as described in Section 7.2.1.1 (see Table 7-1a). Instructions for patients electing to cross-over from placebo to LEE011 at the next scheduled visit:

[figure not shown]
Patients currently receiving placebo plus NSAID plus goserelin and electing to cross-over to LEE011 plus NSAID plus goserelin, can commence LEE011 on Day 1 of their next planned cycle.

Of Note: Patients currently receiving placebo plus tamoxifen plus goserelin and elect to cross-over to the LEE011 arm, must first switch from tamoxifen to an NSAID. At least 5 tamoxifen half-lives (35 days) must elapse, before LEE011 is added. See [Section 6.1](#) for more details.

All patients commencing LEE011 after cross-over from placebo will need to have local hematology, electrolyte and liver function biochemistry tests every two weeks for the first 2 cross over cycles of LEE011 treatment, then at the beginning of cross over cycles 3 to 6, then as clinically indicated, but not less frequently than every 12 weeks. They need to have ECG for QT assessment on the first day before the administration of LEE011. LEE011 should be initiated only in patients with QTcF values <450 msec. The ECGs should be repeated on cross over Cycle 1 Day 15, on cross over Cycle 2 Day 1 and then as clinically indicated. The assessment schedule for patients who will cross-over is presented in [Table 7-1b](#). Consult [Table 6-3](#), [Table 6-4](#) and [Table 6-5](#) for monitoring frequency in cases of hematologic toxicity, liver function abnormalities or QT prolongation respectively.

**Table 7-1a Visit evaluation schedule – Patients that, after protocol amendment 6, continue with their originally randomized study treatment**

Visit name	Category	Reference to Protocol Section	Screening Phase		Treatment Phase							Post-treatment Phase			

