2.1.5 Date of last administration of study treatment

The date of last administration of study treatment is defined as the last date when a nonzero dose of any component of study treatment was administered and recorded on the DAR CRF.

For analyses related to the cross-over period, date of last administration of cross-over open-label ribociclib plus NSAI plus goserelin treatment is defined as the last date when a non-zero

dose of any component of the cross-over open-label ribociclib plus NSAID plus goserelin treatment was administered and recorded on the DAR CRF during the cross-over period.

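### Final SAP 3.5.5 can count Amendment 6 placebo-capsule stops as partial discontinuation of study drug, in the placebo arm only

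*SAP*

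**What the plan says.** The SAP file holds two plans: one for the final CSR, based on protocol amendment 7, and one for the primary PFS analysis, based on amendment 4. The point concerns the final-CSR plan.

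- **Definition.** Section 3.5.5 states that "partial discontinuation is defined as the event when the last non-zero dose of ribociclib/placebo is more than 21 days before the last non-zero dose", here of any study-treatment component, and adds a second condition: "with the permanent discontinuation box checked in the ribociclib/placebo DAR page". Both must hold. Section 3.6.5 of the primary-analysis SAP has the same definition, written when both arms were taking blinded capsules.
- **Last study treatment.** Section 2.1.5 uses "the last date when a nonzero dose of any component of study treatment was administered", so tamoxifen, NSAI or goserelin alone keeps moving this date forward.
- **Period.** Section 3.5.5 summarises partial discontinuation by treatment, and the reasons for stopping each component by arm, over the double-blind on-treatment period. Under section 2.1.8 that period ends 30 days after the last study treatment or on the day before the first cross-over dose, whichever is earlier. Unblinding does not end it.
- **Capsules after Amendment 6.** The amendment text says: "Physical placebo capsules no longer need to be administered but the wording has been kept in places in the protocol to avoid confusion".
- **Placebo patients who stay.** Protocol 7.1 describes "patients in the placebo arm that elect to continue with their current treatment (i.e. endocrine treatment alone").
- **Placebo + tamoxifen patients who cross over.** Protocol 6.1 says: "There needs to be a 35-day (5 half-lives) washout period from tamoxifen before starting LEE011". During the washout they take NSAI and goserelin only.

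**The concern.** Dropping the study-drug capsule while staying on endocrine therapy is normally read as a sign that the patient, or her physician, wanted to be off the study drug. After Amendment 6 a placebo patient can meet that description simply because an inert capsule has lost its purpose. Ribociclib patients continue open-label drug, so no matching event arises in their arm. The final-CSR plan describes unblinding and cross-over as past events, and section 3.5.5 was edited to mention the double-blind period and a cross-over listing. It still has no rule for the capsule withdrawal.

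At stake is a by-arm exposure table in the final CSR. Its placebo column could mix administrative stops with genuine ones. The by-arm reasons for stopping ribociclib/placebo would take in the same stops. That table depends only on the checked box and has no 21-day filter.

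**Working it through.** Section 3.5.5 states no figure to reproduce, so the check applies the rule as logic and then bounds the number of patients.

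**1. The rule.** A patient is flagged if (last non-zero study-treatment date − last non-zero ribociclib/placebo date) > 21 days AND the box is checked.

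- *Placebo, not crossing over.* Take capsules stopped at the amendment date (18-Jul-2019) and endocrine therapy continuing to the Amendment 7 count (08-Jan-2020). The gap is 174 days, and 174 > 21. Flagged if the box is checked, not flagged otherwise.
- *Placebo + tamoxifen, crossing over.* The washout gives a gap of about 35 days, and 35 > 21. Flagged if the box is checked, not flagged otherwise. This takes the last capsule within the double-blind period, before any cross-over ribociclib.
- *Placebo + NSAI, crossing over.* Protocol 7.1 lets these patients start LEE011 on Day 1 of the next cycle. With only the ordinary rest week, the gap is 7 days, and 7 < 21. Not flagged, whatever the box shows.
- *Ribociclib.* Open-label drug continues, so no stop arises from Amendment 6.

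**2. Counts.**

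- Randomised: 672 at 1:1 (final-CSR SAP 1.1). Assumed arm size: 672/2 = 336. Exact arm sizes and the safety-set denominator are not given.
- On treatment at 03-Jul-2019 (Amendment 6): 89 ribociclib + 46 placebo = 135.
- On treatment at 08-Jan-2020 (Amendment 7): 114 in all, "including 79 patients on the ribociclib arm and 35 patients on the placebo arm, of which 8 have crossed-over following Amendment 6". Check: 79 + 35 = 114.
- Non-crossers still on treatment in January 2020: 35 − 8 = 27.
- Most that could be non-crossers: 46 − 8 = 38.

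**3. Possible addition to the placebo rate.** The last column varies the arm size from 326 to 346.

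| Patients flagged | Share of 336 | Range |
|---|---|---|
| 0 (box not checked) | 0% | 0% |
| 27 | 27/336 = 8.0% | 7.8–8.3% |
| 38 | 38/336 = 11.3% | 11.0–11.7% |
| 46 | 46/336 = 13.7% | 13.3–14.1% |

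The ribociclib arm gains 0 in every row.

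**4. How firm the rows are.** The 27 are patients known to have been on placebo-arm treatment nearly six months after the amendment date without having crossed over. The 38 is an upper bound: 46 − 35 = 11 patients left placebo-arm treatment between the two counts, and nothing shows whether their capsules had stopped or whether endocrine therapy then ran more than 21 days. The 46 is a loose ceiling, because it needs all 8 known crossers to be flagged as well. How many of the 8 were on tamoxifen is not stated, so the washout route adds between 0 and 8 patients (8/336 = 2.4%).

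**The case against.** The strongest objection is the checkbox. The rule needs it, and neither document tells sites to check it when placebo is withdrawn. The protocol treats non-crossers as remaining on their allocation, and after Amendment 6 the word placebo denotes that allocation, so a site could reasonably leave the box blank. This stands, and it is why the range starts at zero. It does not remove the point. Protocol 6.1 requires dose changes to be recorded on the dosage record, and SAP 3.5.4 does not count an interruption that never resumes, so permanent discontinuation is a plausible entry. If sites differed, the table would mix conventions.

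A reader might infer that the protocol mandates the stop. It does not: "Physical placebo capsules no longer need to be administered" is permissive, no stop date is given, and the amendment needed ethics approval before implementation.

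A reader might also infer that ribociclib intolerance is masked. The documents do not support that. The ribociclib count is unchanged, and adverse events leading to study drug discontinuation have their own table (SAP 3.7.1.4). Protocol 10.5.3.6 defines tolerability by dose reductions and interruptions due to AE, not by partial discontinuation.

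Component-level reasons by arm help only in part. They do not separate partial from complete stops. The primary-analysis SAP also summarised reasons for partial discontinuation, whereas the final one only lists them, for the cross-over set.

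Finally, the output is descriptive. Protocol 10.7.2 makes every analysis after Amendment 7 descriptive, and the October 2017 primary analysis predates the problem.

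**Conclusion.** The concern holds as a conditional flaw in a descriptive by-arm summary. As written, section 3.5.5 lets Amendment 6 capsule stops, and the washout before cross-over, count as partial discontinuation in the placebo arm only. The addition to the placebo rate is 0 if the box was not checked, about 8 percentage points if it was checked for the 27 known non-crossers, and at most about 11 for non-crossers; 13.7 is a loose ceiling. The same stops can enter the by-arm reasons for ending study drug.

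This rests on 336 patients per arm, on capsules actually being stopped, and on how sites completed the dosage record. The between-arm contrast could narrow or reverse, but no partial-discontinuation rate is given for either arm, so which of these would happen cannot be said. No efficacy result, ribociclib count or AE-discontinuation table is affected. The correction should be made before the final tables are produced, because it is cheap and the count could mislead without it.

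**What to change.** State in final-CSR SAP 3.5.5 how Amendment 6 placebo stops are handled, in one of two ways:

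1. **Symmetric cut.** End the by-arm summaries of discontinuation and partial discontinuation, in both arms, at the Amendment 6 unblinding date.
2. **Reason-based category.** Show placebo stops made solely because of unblinding or cross-over, including the pre-cross-over washout, as a separate administrative category that does not count as partial discontinuation. Keep stops for adverse events or patient decision counted in both arms, and footnote the number reclassified. Use the same category in the by-arm reasons table.

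Dropping every placebo stop after unblinding would be simpler but one-sided: genuine placebo stops would disappear while ribociclib stops over the same months still counted.

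The cost is a short SAP addition and a small derivation change. The first option also takes genuine late ribociclib stops out of the summary. The second depends on the recorded reason being specific enough. Cross-over dates are on the cross-over details CRF page (SAP 2.1.2). The documents do not say where the unblinding date of non-crossers is held, so its source must be confirmed first.
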